The physical risks associated with the NaviCam MCC are generally related to potential non-natural excretion. There is a small risk that the capsule could become stuck in the stomach or small intestine. Based on published and unpublished data of other types of capsule endoscopes, retained capsules have persisted in the GI tract for periods for many years without adverse event. In fact, a large retrospective review by Cheifetz, et al. found that a retained capsule is often asymptomatic or leads to a diagnosis. (Chifetz 2006). Furthermore, the device is made of biocompatible materials and its internal parts are non-toxic. The incidence of capsule retention has been reported to be less than 1% but this figure may be higher in Crohn's disease or other conditions. The rate of surgical/endoscopic removal was noted to be 0.75% (Barkin, 2002).

Patients who are at increased risk of capsule retention are not appropriate study subjects including people with swallowing disorders or with known or suspected gastrointestinal obstructions, strictures or fistulas. In general, if a patient does not pass the MCC naturally through the upper GI tract due to gastroparesis, an EGD will be sufficient to retrieve the capsule. Given that all study patients will receive an EGD as part of their standard work-up for the disease, this does not pose a significant increased risk. Any patient with dysphagia will be excluded because a retained capsule in the esophagus is at risk of aspiration.

Patients will be advised not to have an MRI for 30 days. For patients who are unsure whether they excreted the MCC, *an abdominal X-Ray or "Navicam capsule locator" may be required as an outpatient to confirm passage.*

In order to maximize safety for all study subjects, only consented and enrolled subjects will be administered the MCC under the supervision of a physician and a sub-investigator/trained research associate responsible to the PI. In addition, the MCC will be stored in a secure, limited access area. Product accountability log must include the ¹² protocol number, investigative site name, product name, medical units (i.e., capsules), serial number and subject ID number.

We believe the study poses a low privacy risk to subjects as all data will be encrypted and no PHI will be stored with data. Data will be stored in a REDCap database that allows for the common collection of data from multiple sites.

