Finally, the study has a low economic risk since the device and the interpretation of the device are not being billed to the subject or his/her insurance company. The follow-up EGD is considered standard of care and will be billed to the patient's insurer. AnX Robotica, the manufacturer of the NaviCam has agreed to cover the cost of medical care and treatment for research injuries sustained by subjects enrolled in the study in accordance with the terms of the Clinical Trial Agreement and there is no economic risk expected as a result of unanticipated complications of the device as these will be covered by AnX Robotica, per the final negotiated terms in the Clinical Trial Agreement (currently under negotiation).

Major adverse events that occur will be reported directly to the principal investigator and overall study coordinator within 24 hours. Minor adverse events include inability to tolerate the MCC capsule, discomfort swallowing capsule, issues regarding video capture, issues regarding video transmission, erroneous video interpretation that has no significant impact on clinical care, protocol deviations, reactions to medication (promotility agent), delays in endoscopy interpretation, delays in EGD and others. All minor adverse events will be shared with the entire research team at regularly scheduled monthly calls or sooner at the PI's discretion.

Any major adverse events that occur will be reported directly to the principal investigator who will be available to study subjects 24 hours a day. Severe adverse events will be reported to the entire research team, the sponsor, the DSMB and to IRB within 24 hours. Updates will be provided after a full investigation is completed. SAE's will also be reported to the FDA. Potential major adverse events include delayed definitive care, and capsule retention in the small bowel, and any serious outcome that may be related to study protocol. A DSMB will be formed that includes experts in primary care, emergency medicine, and gastroenterology and research methodology. DSMB of approximately 3-5 multi-disciplinary persons will meet every 6 months during which a report will be produced by PI and as needed for SAE's.

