will be pre-determined, and each area will have a predetermined number of images obtained as suggested by Gastroenterology Society guidelines.

5. Patient data collected will include the following elements: chief complaint of patient, history of present illness, past medical history, current medications (only PPIs and pain medication)..
6. At completion of MCC, video will be archived and patient satisfaction will be assessed. Capsule endoscopy will NOT be used for clinical decisions.
7. Patients will be instructed to return to the physician sooner, if concerning signs develop. A 7 and 30-day follow-up call and chart review is only performed if person is lost to follow-up will be conducted to check for symptom resolution and adverse events.
8. Esophagogastroduodenoscopy (EGD) will be performed as soon as possible in an appropriate endoscopy facility by an experienced endoscopist.
9. Endoscopic images will be stored in secure serve for later comparison with MCC images.

Summary of Research Strategy

- ❖ PRE-SCREEN (DAY -7 to DAY -1)
 - Upper Abdominal Pain or Related Symptoms (Indications for an EGD)
 - Performed in ED, UC, PCP offices or GI clinic
- ❖ SCREEN (DAY -7 -> DAY 0)
 - More thorough screening questions and scheduling by RC (<24 hours)
 - Performed by Telephone
- ❖ ENROLL (DAY 0)
 - Signed Informed Consent procedure, more detailed questions and MCC Procedure performed
 - Occurs at the GWU Medical Faculty Associates Building on [name].
 - NaviCam MCC performed by trained Clinician.
 - Reviewed by a Gastroenterologist.
 - Scheduled for an EGD will ideally be performed within 5 days of the MCC procedure, but will allow MCC procedure to be performed up to 14 days either before or after an EGD (paid by insurance as standard of care).
- ❖ FOLLOW-UP (DAY 1-30)

- Day 7 and Day 30: Telephone Call plus CRISP Chart Review, only if lost to follow-up.

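### Section 6.3.1 ends the MRI warning at a fixed 30 days without tying it to confirmed passage of the capsule

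*Protocol*

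**What the plan says.** Section 6.3.1 names non-natural excretion as the main physical risk of the capsule. It gives one instruction on MRI: "Patients will be advised not to have an MRI for 30 days". The next sentence deals with participants who are unsure whether the capsule has left. For them an abdominal X-ray or the capsule locator "may be required as an outpatient to confirm passage". That sentence has a trigger, a method and a purpose, but no day by which the check is done.

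The same section describes how retention behaves. Of experience elsewhere it says: "other types of capsule endoscopes, retained capsules have persisted in the GI tract for periods for many years without adverse event". Citing a retrospective review, it adds that "a retained capsule is often asymptomatic or leads to a diagnosis". It also states: "Potential major adverse events include delayed definitive care, and capsule retention in the small bowel".

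The remaining pieces lie in other sections:

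- Section 8.3.7, on patient satisfaction, points to the Magnet 7 and 8 forms (Days 7 and 30). It includes a yes/no item on whether the participant noticed the capsule pass.
- Section 9.4, step 7: "Patients will be instructed to return to the physician sooner, if concerning signs develop". The Day 7 and Day 30 follow-up "will be conducted to check for symptom resolution and adverse events".
- Section 4 gives a subject duration of 30 days.
- Section 10.2, criterion 10, excludes people who expect an MRI within 30 days.

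**The concern.** A warning that ends on a date protects the participant only if the capsule has gone by then. On the protocol's own account of retention, neither reaching Day 30 nor feeling well shows that it has. Followed as written, 6.3.1 lets a participant whose passage was never confirmed reach the end of the study just as the MRI advice runs out.

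This is a question of participant safety. It belongs in the protocol and is not a detail that a statistical analysis plan would supply. No estimate for Aims 1 to 3 depends on it. At stake is whether a participant who may still carry the capsule is told to keep avoiding MRI, and whether anyone is assigned to find out.

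**Working it through.** The protocol gives no figure to reproduce here, so the check sets the stated rules side by side and follows one participant through them.

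**1. When does the warning end?** At Day 30 (6.3.1). The exclusion in 10.2 uses the same window, and the subject duration in section 4 is also 30 days. Planned follow-up and the warning therefore end together.

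**2. What would show that the capsule has gone?** Two things: the participant's report (8.3.7) and the X-ray or locator (6.3.1). The report is sought at Day 7, which is 30 − 7 = 23 days before the warning ends, and again on the day it ends.

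**3. What follows if the participant did not notice passage?** Section 8.3.7 attaches no action. Section 6.3.1 says a check may be needed for those who are unsure, but does not name the calls as the point where they are identified and sets no deadline. Step 7 of 9.4 gives the purpose of the contacts as symptoms and adverse events and does not mention passage. Neither 6.3.1 nor 9.4 extends the MRI advice while passage is in doubt.

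**4. Does the EGD settle it?** Not dependably, for three reasons.

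- *Order:* the research summary in 9.4 prefers an EGD within 5 days of the capsule but "will allow MCC procedure to be performed up to 14 days either before or after an EGD". An EGD done first says nothing about a capsule swallowed later.
- *Occurrence:* 6.3.1 assumes every participant will have an EGD, while 13.2 speaks of referral and expects drop-out.
- *Reach:* an EGD examines the upper tract and does not exclude retention in the small bowel, which is the site 6.3.1 lists as a potential major adverse event.

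**5. Does adverse-event reporting settle it?** No. It governs what happens once a retention is known and does not find one.

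**6. How large is it?** The event that matters needs a chain:

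P(MRI with capsule inside) = P(retained) × P(still inside and not detected after Day 30, given retained) × P(MRI in that time, given both).

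The protocol informs only the first term: retention has been reported at less than 1%. With 72 capsules (13.2) that is fewer than 72 × 0.01 = 0.72 expected retentions of any kind, if the reported rate applies here. The other two terms do not appear in the protocol. All that can be said is that the product is smaller than the first term.

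**The case against.** The strongest reply is that the route already exists in outline. The Day 7 question is dated, does not depend on symptoms and finds people with unwitnessed passage about three weeks before the warning ends. The X-ray or locator sentence tells the reader that some participants will need imaging, and why. In a narrative of risks, what is missing is a link and a deadline. The instructions participants actually receive would normally be in the consent form, and any action on a negative answer would be on the Magnet 7 and 8 forms. Neither is shown. Section 10.2 also removes many people at higher risk of retention (Crohn's disease, gastroparesis, suspected obstruction, altered anatomy) and those who expect an MRI within the window.

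Most of this stands, and it rules out three stronger readings.

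- A reader might infer that every other safeguard waits for symptoms or a detected event. Section 8.3.7 shows otherwise.
- A reader might infer that the passage check is left to choice. The wording makes it conditional on uncertainty and allows that it may be required. Its weakness is the missing date and link.
- A reader might compute 1 − 0.99^72 = 51.5% and take it as the chance of harm. That is the chance of any retention at the ceiling of the reported range. At an assumed 0.1% the same formula gives 7.0%. Neither figure is the chance of an MRI with a capsule inside.

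The reply does not remove the rule that is stated. The warning has a fixed end, and no visible sentence makes that end depend on passage.

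**Conclusion.** The point holds as a minor one. Section 6.3.1 sets a rule that its own description of retention does not support, because time alone does not show that the capsule has gone. The question and the check that would repair the rule are both in the protocol, unconnected to each other and to the MRI advice.

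The chance of harm is small and cannot be derived from the document. The efficacy results are unaffected, and 30 days as a minimum is not disputed. The conclusion assumes that the unseen consent pages and the Magnet 7 and 8 forms do not already supply the link. If they do, all that remains is to carry the rule into the protocol. It also takes the MRI hazard as given: the protocol does not describe it, but the warning and exclusion criterion 10 imply it.

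**What to change.** In 6.3.1 and 9.4:

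- State that the MRI warning lasts at least 30 days **and** until passage of the capsule is confirmed.
- Make the passage question in 8.3.7 the trigger. A participant who remains unsure at the Day 7 or Day 30 call has the check 6.3.1 already allows, by about Day 30. Prefer the locator, to avoid radiation, and otherwise use the X-ray.
- Keep the warning in force and the participant in safety follow-up until an unconfirmed case is resolved.
- State that an EGD counts towards confirmation only if it was done after the capsule, and only for the upper GI tract.

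The cost is a few sentences, a few extra locator or X-ray checks (the number cannot be worked out from the protocol) and a few participants followed past Day 30. The sample size and the analyses do not change.

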8. STUDY OUTCOME MEASURES

8.1. Primary Outcome:

Aim 1: Pilot and Feasibility Stage.

- 1) *Implementation:* Installation, Training, Site Requirements
- 2) *Practicality:* Duration of MCC test (minutes), Technician “learning curve,” Clinical Staff and Patient Satisfaction, Duration of fasting required
- 3) *Integration:* Scheduling MCC, Linkage with EGD follow-up, Image storage, Image transfer, Documentation of Interpretation, Photo-documentation, Database development

Aim 2: High-Quality Visualization (90%) of Gastric Anatomic Landmarks

Defined as visualization and photo-documentation of the following anatomical landmarks:

- 1) Lower Esophagus / Z line
- 2) Cardia / fundus
- 3) Body, lesser curvature AND/OR Body, greater curvature
- 4) Anterior / Posterior walls
- 5) Angularis
- 6) Antrum
- 7) Pylorus
- 8) Duodenal Bulb
- 9) Duodenal Ampulla

Aim 3: MCC versus EGD for visualization of anatomic landmarks (see above) and gastric lesions in symptomatic patients

Defined as visualization and photo-documentation of the following structures and diseases:

- 1) Visible Lesions (Paris Classification if relevant)
- 2) Ulcers (Forrest Classification) erosions
- 3) Gastric Atrophy
- 4) Gastric Varices
- 5) Gastritis*
- 7) Submucosal lesions
- 8) “Does patient need a follow-up EGD?” Y/N (Opinion of endoscopist interpreting MCC based on MCC findings.)

* (not erythema but ‘chicken wire’ pattern intramucosal change in vascular pattern or hemorrhagic)

8.2. Secondary Outcomes:

- (1) Cost-effective analysis

- (2) 30-day follow-up for adverse events and safety
- (3) Patient Satisfaction of MCC versus EGD
- (4) Replication of similar sensitivity and specificity of MCC to EGD to prior trials outside of the US for (a) Ulcers; (b) Cancer; (c) Inflammatory Changes
- (5) Time spent visualizing the stomach for MCC versus EGD (minutes)
- (6) Visualization of the duodenum
- (7) Hiatus hernia

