12.2. Assessment of Adverse Events

All adverse events will be graded for severity as follows:

Mild: Sign or symptom, usually transient, requiring no special treatment and generally not interfering with usual activities.

Moderate: Sign or symptom, which may be ameliorated by simple therapeutic measures; yet, may interfere with usual activity.

Severe: Sign or symptom that are intense or debilitating and that interfere with usual activities. Recovery is usually aided by therapeutic measures.

The relationship of the adverse event to the study device is defined as follows:

Probably related: Follows a reasonable temporal sequence from study device use delivery/retrieval and cannot be reasonably explained by known characteristics of the subject's clinical data.

Possibly related: Follows a reasonable temporal sequence from study device delivery/retrieval but could have been produced by the subject's clinical state regardless of the study device.

Not related: No relationship to study device activation is perceived.

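### Section 6.3.1 classes six technical or logistic items as minor adverse events, which the section 12.2 severity scale cannot grade and which the 30-day safety outcome does not exclude

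*Protocol*

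**What the plan says.** Section 6.3.1 of the protocol gives the minor class as an open list. It begins "Minor adverse events include inability to tolerate the MCC capsule, discomfort swallowing capsule, issues regarding video capture, issues regarding video transmission", continues with misreads that do not significantly affect care, and ends with "protocol deviations, reactions to medication (promotility agent), delays in endoscopy interpretation, delays in EGD and others". The same section has a major class: "Potential major adverse events include delayed definitive care", together with small-bowel capsule retention and serious outcomes that may be related to the protocol.

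Section 12.2 states: "All adverse events will be graded for severity as follows". Its lowest level reads "Mild: Sign or symptom, usually transient, requiring no special treatment and generally not interfering with usual activities". The moderate and severe levels also start from a sign or symptom.

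Section 8.2 names the safety outcome as "30-day follow-up for adverse events and safety", without limiting it to clinical events. Section 7.2 lists 30-day safety as a secondary objective.

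**The concern.** Section 12 defines unanticipated events (12.1) and serious events (12.3) but gives no general definition of an adverse event. The list in 6.3.1 is therefore the nearest thing to a working definition, and it mixes effects on the participant with failures of equipment, reading, scheduling and conduct.

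Two things are at stake. Site staff are told to grade events that no grade describes. And the 30-day outcome, taken at its word, has no boundary between a clinical effect and a logistic failure, so its meaning depends on a choice the protocol does not make.

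**Working it through.** There is no figure to reproduce: section 13.2 says the 72 participants were chosen on practical grounds and that no formal inference is planned. The check sets the passages side by side.

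**Step 1. Can each item named as minor in 6.3.1 be graded under 12.2?**

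| Item in 6.3.1 | Sign or symptom? | Nearest other place in the protocol |
|---|---|---|
| Cannot tolerate capsule | Yes, or closely tied to one | – |
| Discomfort on swallowing | Yes | Satisfaction questions, 8.3.7 |
| Reaction to medication | Yes | – |
| Video capture fault | No | Photo-documentation, Aim 1 (8.1) |
| Video transmission fault | No | Image transfer, Aim 1 (8.1) |
| Misread, no significant clinical impact | No | MCC against EGD, Aim 3 (8.1) |
| Protocol deviation | No | Section 19.5; form Magnet 11 |
| Interpretation delay | No | Documentation of interpretation, Aim 1 (8.1) |
| EGD delay | No | EGD linkage, Aim 1 (8.1) |

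Three of nine can be graded and six cannot. Section 12.2 makes no exception for the six.

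**Step 2. Are the six handled separately elsewhere?** Deviations are: 19.5 gives them their own source documentation, and Appendix B gives them Magnet 11, while adverse events go on Magnet 10. Neither place says deviations are left out of the adverse event count, so the protocol treats them both as adverse events and as something apart. Appendix B lists no dedicated form for video faults, misreads or EGD delays; Magnet 12 covers only loss to follow-up. A failed image transfer or a late EGD can therefore be both an Aim 1 result and an adverse event.

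**Step 3. How wide is the misread item?** It covers misreads without significant clinical impact. Section 9.4 says capsule findings will not be used for clinical decisions, so most misreads would meet that condition. An error of reading, which is accuracy information, would then also be an adverse event.

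**Step 4. Reporting.** Section 12.3 sends adverse events to the PI, the IRB and the sponsor within 24 hours. Section 6.3.1 has minor events shared with the research team at monthly calls, or sooner at the PI's discretion. Section 19.5 sends deviations to the PI within 24 hours. A protocol deviation falls under all three rules.

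**Step 5. Delay.** EGD delay is named as minor and delayed definitive care as potentially major, with no stated criterion separating them. Late EGDs are foreseeable: section 9.4 aims for 5 days but allows 14 days either side.

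**The case against.** The strongest reply is that 6.3.1 is a risk section, not an analysis rule. The only use it states for the minor list is discussion on team calls. Nowhere does the protocol say that an adverse event rate will be computed from that list or that minor and clinical events will be pooled. Tabulation is normally left to a SAP, which is not at hand and could separate them. Separate forms for deviations and for loss to follow-up also point towards separate tabulation. This stands, and it limits the point to what the wording permits.

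A reader might go further and infer that the safety result will be inflated by logistics, that real harm will be diluted, or that comparison with other capsule studies is lost. The documents do not support this. Adding minor items removes no clinical event. Major events are a separate class, serious events have their own definition and reporting route, and relatedness to the device is classified. How other studies defined adverse events is not described, and no event counts are given from which an inflated rate could be estimated.

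Nor is delayed EGD plainly put in two classes. The two terms differ, and 6.3.1 can be read as separating them by consequence, as it does for misreads. What remains is that the dividing line is not written down.

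On reporting, the 24-hour sentence sits under the serious-event heading, and its recipients differ from those of the monthly calls, so both could be followed. But the next sentence of 12.3 speaks of additional procedures for serious events, which suggests the first covers all adverse events. On that reading every video fault goes to the IRB and the sponsor within 24 hours, which is hard to square with the monthly route.

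None of this removes the mismatch between 6.3.1 and 12.2. It is stated in the protocol, and a SAP cannot settle the definition, grading and reporting that site staff must follow.

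**Conclusion.** The point holds as a conflict of definition. Six of the nine named minor adverse events are technical or logistic and cannot be graded as section 12.2 requires. Deviations are also recorded separately, and the reporting passages are not aligned. Read literally, the 30-day outcome can include these items; whether it would in practice is not stated.

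The size is modest. Safety is a secondary, descriptive outcome in a proof-of-concept study, no primary aim is affected, and major and serious events remain identifiable. The conclusion assumes that section 12 is applied as written and that no definition outside the protocol narrows the term. It is still worth correcting, because the safety result is easier to interpret when its events are all clinical.

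**What to change.** - In 6.3.1 and section 12, limit the term adverse event to untoward medical occurrences in the participant, so that the 12.2 scale applies to every event it covers.
- Report the six items outside the 30-day adverse event count: video faults as device deficiencies, misreads under Aim 3, interpretation and EGD delays under Aim 1, and deviations on Magnet 11.
- Reconcile the entries for EGD delay (minor) and delayed definitive care (major), so that one occurrence falls in one class by a written criterion.
- Reconcile 6.3.1 with 12.3, and with 19.5 for deviations, on who is told and when. The investigators and the sponsor should decide which timing applies.

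The cost is rewording and one extra table. Every item is still collected, so no data are lost.

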8.3. Selected Outcomes Measures (see data collection sheets)

8.3.1. Procedure time.

- When measuring procedure time of EGD and MCC, we will consider all components of procedure including anesthesia, prep, cleaning and preparing room for next patient and turn-around time. We will also measure total time for staff and for the clinician.

8.3.2. Training to perform MCC.

- How long? How many cases needed? Is there a learning curve to speed and accuracy?

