22. APPENDICES

22.1. APPENDIX A: Schedule of Events

2019-2021

- Consensus building, Protocol Development, FDA letter IRB submission (+/- IDE)
- Contract between primary sites GWU MFA and AnX Robotica
- DSMB formation, steering committee convene, central MCC reading team call schedule established for January 2020 to January 2021; hiring of staff
- MCC training and Site Visit by PI and team
- Enrollment kick off
- Monthly Calls for entire team, Status reports
- Target Enrollment Reached, End recruitment DSMB report prepared
- Data Cleaning
- First manuscript Draft Prepared
- Manuscript Submitted (To be discussed: Dissemination plan)

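### Section 6.3.1 shares erroneous MCC interpretations with the whole research team monthly during enrollment and exempts neither MCC readers nor operators, so EGD results or the other reader's findings could reach people still producing reads

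*Protocol*

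**What the plan says.** The protocol's Section 6.3.1 lists the minor adverse events. Most are practical or clinical: tolerance, swallowing discomfort, video capture and transmission, delays. One concerns the diagnostic result itself: "erroneous video interpretation that has no significant impact on clinical care". The rule for the whole list is: "All minor adverse events will be shared with the entire research team at regularly scheduled monthly calls", or sooner if the PI so decides.

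Appendix A (Section 22.1) includes "Monthly Calls for entire team, Status reports" after the enrollment kick-off and before target enrollment is reached. The same appendix refers to a "central MCC reading team call schedule established for January 2020 to January 2021". It does not say that this reading team stands outside the entire team.

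Section 9.4, step 6, states: "Capsule endoscopy will NOT be used for clinical decisions". Step 9 of the same section states: "Endoscopic images will be stored in secure serve for later comparison with MCC images", with no date for the comparison. The research strategy summary in Section 9.4 aims for EGD within 5 days of MCC and allows up to 14 days in either order. It has a clinician perform the MCC and a gastroenterologist review it.

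Section 8.3.6 relies on two independent readers. Section 8.3.2 asks about training: "Is there a learning curve to speed and accuracy".

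**The concern.** The minor-event rule treats a misreading like a sore throat after swallowing: it is told to everyone, soon. For most items on the list that is harmless. A misreading is different, because it is outcome data. To report one is to say that a given read was wrong, and usually why. If those who hear it are still performing or reading MCC, their later reads may be shaped by results that an accuracy study would normally keep from them.

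Masking a reader to the same participant's EGD would not close this route, since the information comes from other, earlier participants.

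Three outputs are exposed:

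- **Aim 3 and Section 8.2(4).** Agreement, sensitivity and specificity could describe readers who received feedback during the trial, while the stated purpose is comparison with trials outside the US.
- **Section 8.3.2.** The accuracy learning curve could mix ordinary experience with disclosed answers. The analysis could not separate the two afterwards, so the number of cases needed might not carry over to a setting without such feedback.
- **Section 8.3.6.** The two readers are meant to be independent, so that a lesion that healed before EGD can be told from an MCC false positive. Telling one reader the other's findings would weaken that.

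Aim 2 (visualization of landmarks) does not use EGD as its reference and is largely unaffected.

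**Working it through.** **1. Does the text open the route?** Four statements combine.

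- A misreading without significant effect on care is a minor event (6.3.1).
- MCC does not guide care (9.4, step 6), so nearly every misreading falls in that class.
- All minor events go to the entire team monthly or sooner (6.3.1).
- The calls run during enrollment (Appendix A).

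No section exempts readers or operators, delays disclosure until reads are locked, or states that readers are masked to EGD. The route is open.

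**2. Accrual.** The Protocol Summary gives 2 to 3 participants per week over 30 weeks, that is 2 × 30 = 60 to 3 × 30 = 90. The planned 72 needs 72 / 30 = 2.4 per week, which is consistent. Section 13.2 says that 72 was chosen on practical grounds, so there is no power calculation to reproduce.

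**3. Share examined after the first call.** Assume even accrual, a month of 4.345 weeks, and a first call one month after enrollment starts.

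- Before the first call: 2.4 × 4.345 = 10.4 participants.
- After it: 72 − 10.4 = 61.6, about 62 of 72 (86%).
- Calls within accrual: 30 / 4.345 = 6.9, so 6 complete months.

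The protocol also gives 12 months to completion (Protocol Summary) and a recruitment and follow-up window from November 2019 to October 2021, 24 months (19.3). If accrual filled those periods, the share would be (72 − 72/12) / 72 = 66/72 = 92%, or (72 − 72/24) / 72 = 69/72 = 96%. Both windows include time other than recruitment, so these are upper values.

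**4. Would EGD results exist by the first call?** If EGD takes the full 14 days (2 weeks), it is complete for participants examined in the first 4.345 − 2 = 2.345 weeks: 2.4 × 2.345 = 5.6 of the 10.4. If it takes 5 days (0.714 weeks): 2.4 × 3.631 = 8.7. This assumes that everyone attends within the window, and Section 13.2 expects some drop-out. So EGD results would usually be on file; whether anyone would have compared them with MCC by then is not stated.

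**5. Size of effect.** The protocol gives nothing from which to derive one. If feedback raised sensitivity by an assumed d after the first call, the pooled figure over 30 weeks would move by 0.855 × d: nil for d = 0, and 1.7, 4.3 or 8.6 points for d = 2, 5 or 10. These values of d have no source and only show how the shift scales.

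**The case against.** A reader might go further and infer that an MCC read can be called erroneous only against EGD, that the rule therefore requires a running MCC-EGD comparison, and that readers are told their errors and later reads are trained on the reference. The documents do not support this.

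- **Standard of error.** The two readers, the gastroenterologist's review, and separate MCC assessment forms (Magnet 4 and 5) beside the EGD form (Magnet 6) are other ways for an error to surface.
- **Timing.** Step 9 of Section 9.4 keeps EGD images for an undated later comparison. If that follows enrollment, the calls carry little or no reference information.
- **Content.** The protocol does not say what is disclosed. A call could report only a count.

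These points stand, and they limit the finding to a possible route. They do not close it. If error means disagreement between readers, sharing it bears on their independence instead. The undated comparison does not override an explicit monthly rule for all minor events.

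It is also fair to say that few errors would be shared. Take 30% of participants as positive, an assumption guided by the 70% negative figure that Section 6.2 gives for patients without alarm symptoms, and an assumed sensitivity of 80%. Missed cases per monthly call are then 10.4 × 0.30 × 0.20 = 0.6, and 72 × 0.30 × 0.20 = 4.3 in the whole study. With 50% positive, the figure is 10.4 × 0.50 × 0.20 = 1.0 per call. A steady rise in accuracy from about one missed case a month would be hard to credit, although false positives and the several lesion types in Section 8.3.5 would add to the count.

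Finally, this is a proof-of-concept study with no formal inference planned (13.2), and feedback during early use can be a legitimate choice in a pilot. That lowers the weight. It does not help the protocol's own aims of replicating published accuracy and measuring a learning curve.

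**Conclusion.** The concern holds as an open feedback route. Section 6.3.1 sends erroneous interpretations to the entire team during enrollment and contains no exception for those who perform or read MCC. About 62 of 72 participants (86%) would be examined after the first call, given even accrual over 30 weeks and calls that start one month in.

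That figure measures opportunity only. Whether any reference result would be passed on, and how much it would change later reads, cannot be known from the protocol, so no particular inflation of sensitivity can be claimed.

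The weight is modest: estimates are at stake, not a formal test, and Aim 2 is largely untouched. It is worth correcting because the correction is cheap and the effect, if it occurred, could not be removed in analysis.

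**What to change.** Add an exception to Section 6.3.1, for example: Erroneous MCC interpretations, and discordances between MCC and EGD or between MCC readers, are recorded on the study forms and are available to the DSMB, and to the PI if the PI does not read MCC. They are not shared with MCC readers or operators on the team calls, or sooner, until all MCC reads are complete and locked. All other minor adverse events remain on the monthly calls.

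The exception covers only errors without significant effect on care; the reporting of major and serious events is unchanged. No separate recording staff are needed. If the PI does read MCC, the sentence in Section 12.3 that sends adverse events to the PI within 24 hours should be aligned with the exception.

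The cost is one sentence in 6.3.1 and the loss of error feedback to readers during the trial. Participants' care is unaffected, because MCC results do not guide it.
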